6.2.5.2 Secondary Outcomes

Secondary Outcomes: Total Number of Days Spent in Hospital

Total number of days spent in the hospital will be calculated by two methods for the FAS population. First, LOS will be calculated by inpatient stays only and second, LOS will be calculated by inpatient stays including time spent in prolonged observation status (>1 day). Descriptive statistics for total number of days spent in hospital will be shown in a table by initial care, follow-up, and overall for the pre-period and post-period, and depicted graphically overall using box plots. Patient counts and percentages will be given for the primary outcome (e.g., 0 day, 1 day ... > 5 days). Descriptive statistics in the table will be repeated by patients who complete the study or are admitted for comparison. No formal hypothesis testing will take place.

Secondary Outcomes: Infection-Related Total Admitted Hospital Days

Infection-related total admitted hospital days will be calculated by two methods by the pre-period and post-period for the FAS population. First, LOS will be calculated by inpatient only stays and second, LOS will be calculated by inpatient stays including time spent in prolonged observation status (>1 day). The infection-related total admitted hospital-days will be assessed using a similar approach described for the primary analysis and will limit to patients who had infection-related hospital stays. Tables will reflect descriptive statistics for infection-related hospital stays and depicted graphically overall using box plots. Summaries will be repeated for only patients that are admitted. No formal hypothesis testing will take place.

Secondary Outcomes: ED Length of Stay at Initial Episode of Care

Tables will reflect descriptive statistics for ED length of stay at the initial episode of care by the pre-period and post-period for the FAS population. No formal hypothesis testing will take place.

Secondary Outcomes: Infection-Related Major Surgical Interventions that Required Operating Room Time

Infection-related major surgical interventions that required operating time will be displayed in tables by initial care, follow-up, and overall by the pre-period and post-period for the FAS population. Patient counts and percentages will be reported for no, any, expected, and unexpected surgical interventions. No formal hypothesis testing will take place.

Secondary Outcomes: Infection-Related Hospitalizations

Infection-related hospitalizations will be displayed in tables by initial care, follow-up, and overall by the pre-period and post-period for the FAS

population. Patient counts and percentages will be reported for none, any, 1, 2, and ≥ 3 infection-related hospitalizations. No formal hypothesis testing will take place.

Secondary Outcomes: Infection-Related Hospitalizations that Resulted in Admission to Intensive Care Unit (ICU)

Infection-related hospitalizations that resulted in admission to ICU will be displayed in tables by initial care, follow-up, and overall by the pre-period and post-period for the FAS population. Patient counts and percentages will be reported for none, any, 1, 2, and ≥ 3 infection-related hospitalizations that resulted in admission to ICU. No formal hypothesis testing will take place.

Secondary Outcomes: All Cause Hospitalizations in the 30 Days Post-Discharge from the Hospital or Release from ED

All-cause hospitalizations in the 30 days post-discharge from the hospital will be displayed in tables by the pre-period and post-period for the FAS population. Patient counts and percentages will be reported for none, any, 1, 2, and ≥ 3 all-cause hospitalizations in the 30 days post-discharge from the ED. No formal hypothesis testing will take place.

Secondary Outcomes: Infection-Related ED Visits

Infection-related ED visits will be displayed in tables by initial care, follow-up, and overall by the pre-period and post-period for the FAS population. Patient counts and percentages will be reported for none, any, 1, 2, and ≥ 3 infection-related ED visits. These categories will be repeated for all, expected, and unexpected ED visits. No formal hypothesis testing will take place.

Secondary Outcomes: Infection-Related Outpatient Healthcare Visits

Infection-related outpatient healthcare visits will be displayed in tables by initial care, follow-up, and overall by the pre-period and post-period for the FAS population. Patient counts and percentages will be reported for none, any, 1, 2, and ≥ 3 infection-related outpatient healthcare visits. These categories will be repeated for all, expected, and unexpected outpatient healthcare visits. No formal hypothesis testing will take place.

Secondary Outcomes: Use of PICC Line or Central Line to Administer Antibiotic Therapy

Use of PICC line, central line or no line to administer antibiotic therapy will be displayed in tables by initial care, follow-up, and overall by the pre-period and post-period for the FAS population. Patient counts and percentages will be presented. No formal hypothesis testing will take place.

Secondary Outcomes: Infection-Related Healthcare Visits Due to PICC Line or Central Line Used to Administer Antibiotic Therapy

[REDACTED]

Infection-related healthcare visits due to PICC line or central line used to administer antibiotic therapy will be displayed in tables by initial care, follow-up, and overall by the pre-period and post-period for the FAS population. Patient counts and percentages will be reported for none, any, 1, 2, and ≥ 3 infection-related outpatient healthcare visits. These categories will be repeated for all, expected, and unexpected outpatient healthcare visits. No formal hypothesis testing will take place.

Secondary Outcomes: Serious Adverse Events

Serious adverse events will be reported in a table as presented in section 6.2.9. No formal hypothesis testing will take place.

Secondary Outcomes: Patient Satisfaction with Care

Descriptive statistics for the patient satisfaction questionnaire will be reported within a table by the pre-period and post-period for the FAS population. No scoring or formal hypothesis testing will take place. A listing will display the date of visit the assessment occurred, questions answered, and the response to each question for each patient.

Secondary Outcomes: Patient Work and Productivity Loss

Descriptive statistics for the WPAI questionnaire will be reported in a table by the pre-period and post-period for the FAS population. Summaries will describe the distribution of scores derived at day 14. Scores will be calculated and summarized following the WPAI Score Guidelines (see Appendix D). A listing will display the date of visit the assessment occurred, component scores (absenteeism, impairment while working, overall work impairment, activity impairment), questions answered, and the response to each question for each patient. No formal hypothesis testing will take place.

Secondary Outcomes: Patient HRQoL

Descriptive statistics for the SF-12 will be reported within a table by the pre-period and post-period for the FAS population. Summaries will describe the distribution of scores derived at baseline and day 14, as well as the distribution of changes in scores from baseline. Scores will be calculated and summarized following the SF-12 scoring manual (see Appendix E). A listing will display the date of visit the assessment occurred, component scores (mental health and physical), questions answered, and the response to each question for each patient.

[REDACTED]

[Redacted]

[Redacted]

[Redacted]

[Redacted]

[Redacted]

[Redacted]

[Redacted]

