7.0 List of Potential Tables/Listings/Figures

Table shells are included in the file 055123_ADVANCE_SAP_Table Shells_v 1.0_20181204.docx.

§ Denotes output that can be produced at interim analysis. f Denotes the minimum output necessary to support sample size confirmation. * Denotes output to be produced only for the sample size confirmation described in the protocol.

Table 1 Disposition of Study Patients by Site and All Patients: Enrolled Set§f
Table 2 Study Site Characteristics §
Table 3.1 Patient Demographics at Baseline by All Patients: Enrolled Set§
Table 3.2 Patient Demographics at Baseline by Site 10X: Full Analysis Set
Table 4 Comorbid Conditions Reported at Baseline: Full Analysis Set§
Table 5 Healthcare Resource Utilization at Previous 3 Months: Full Analysis Set§
Table 6 Infection characteristics and clinical characteristics during the initial assessment in the ED: Full Analysis Set§
Table 7.1 Care Pathways of Patients Following Initial Episode of Care: Full Analysis Set§
Table 9 Use of Antibiotics by Patients During the Study: Full Analysis Set§
Table 10 Primary Outcome: Hospital Admission Rate at Initial Episode of Care Full Analysis Set§f
Table 11 Primary Outcome: Primary Outcome: Hospital Admission Rate at Initial Episode of Care Multivariate Analysis Full Analysis Set§f
Table 12.1 Secondary Outcome: Total LOS during Initial Care and Follow-up: Full Analysis Set§f
Table 12.XX Secondary Outcome: Total LOS during Initial Care and Follow-up: Full Analysis Set: Site XXX§f
Table 13.1 Secondary Outcomes by All Patients: Full Analysis Set§
Table 13.2 Secondary Outcomes: Infection-related outpatient healthcare visits by Site 101: Full Analysis Set
Table 13.XX Secondary Outcomes: Infection-related outpatient healthcare visits by Site 10X: Full Analysis Set
Table 14 Secondary Outcome: Serious Adverse Events by SOC and PT: Full Analysis Set§
Table 15 Secondary Outcomes: Patient Satisfaction with Care: Full Analysis Set §
Table 16 Secondary Outcomes: Patient Work and Productivity Loss: Full Analysis Set§
Table 17 Secondary Outcomes: Patient Health-Related Quality of Life (SF-12): Full Analysis Set
Table 18 Other Outcomes: Full Analysis Set§
Table 19 Adverse Events- Overall Summary: Full Analysis Set§
Table 20 All Adverse Events by SOC and PT: Full Analysis Set§
Table 21 Adverse Events with Possible Causal Relationship to Study Drug by SOC and PT: Full Analysis Set§

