Table 22 Adverse Events Leading to Study Discontinuation by SOC and PT: Full Analysis Set§
Table 23 Adverse Events Leading to Death by SOC and PT: Full Analysis Set§
Table 24 Laboratory Values: Full Analysis Set§
Table 25 Microbial Assessments: Full Analysis Set§
Table 26 Vital Signs: Full Analysis Set§
Table 27 Summary of Cost Analyses over 44 Day Period: Full Analysis Set
Table 28 Sample Size Confirmation f*
Table 29 Sample Size Confirmation with Variations of Power and Statistical Significance *
Table 30 Secondary Outcome: ED LOS during Initial Care and Follow-up: Full Analysis Set*

Figure 1 Box plot of all-cause hospitalization time during initial care and follow-up by period: Full Analysis Set

Figure 2 Box plot of infection-related hospitalization time during initial care and follow-up by period: Full Analysis Set

Listing 1 Patient Disposition: Enrolled Set§

Listing 3 Patient Demographics at Baseline: Enrolled Set§

Listing 4.1 Medical History at Baseline Visit: Enrolled Set, Part 1§

Listing 4.2 Medical History at Baseline Visit: Enrolled Set, Part 2§

Listing 4.3 Medical History at Baseline Visit: Enrolled Set, Part 3§

Listing 4.4 Medical History at Baseline Visit: Enrolled Set, Part 4§

Listing 5 Infection Characteristics at Baseline: Enrolled Set§

Listing 6 Antibiotic Usage: Enrolled Set §

Listing 7 Prior Non-Antibiotic Usage for Chronic Conditions Reported at Baseline: Enrolled Set§

Listing 8 Hospitalization, ED and Observation Unit Visits: Enrolled Set §

Listing 9 Hospitalization Length of Stay: Enrolled Set §

Listing 10 Other Healthcare Visits: Enrolled Set§

Listing 11 SF-12 Questionnaire at Baseline and Day 14: Enrolled Set

Listing 12 Patient Satisfaction Survey at Day 14: Enrolled Set

Listing 13 WPAI at Day 14: Enrolled Set

Listing 14 Surgical Interventions and Procedures: Enrolled Set§

Listing 15 Adverse Events: Enrolled Set§

[figure not shown]
Listing 16 Laboratory Results: Enrolled Set§

Listing 17 Microbial Assessments: Enrolled Set§

Listing 18 Vital Signs and Physical Examination at Follow-up: Enrolled Set§

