Secondary Outcomes (All visits)	Hospitalization LOS (days)	
For all-cause: Σ (Hospitalization end date – Hospitalization start date +1), when both dates are available. If ongoing at end of study or discontinuation date, use study completion date or discontinuation date as end date. For outcomes, LOS will be computed two ways: only in-patient hospitalizations visits and inpatient hospitalizations visits with prolonged observation

[figure not shown]
Analysis Section (Visit)	Variable (Units)	Definition
		
status (e.g., time in observation status exceeds 1 day).
 
For infection-related: Subset all-cause hospitalization time for patients with infection-related hospitalization stays

Secondary Outcomes (End of Study Visit)	Completers Flag	
If "Did the patient complete the study?" = 1 on the end of study visit CRF page and date of study completion does not equal missing, then =Yes, Else = No
 
This flag will be used to repeat certain primary and secondary outcomes that could be influenced by early discontinuation (e.g., LOS)

Secondary and Other Outcomes (Initial episode of care)	ED LOS (hours) Observation Status LOS (hours)	
Impute with estimated time where applicable for partial times. if admission date = discharge date then LOS (hours) = discharge time - admission time
 
else LOS (hours) = sum all hours over stay, with a full day counting as 24 hours

Secondary Outcomes (Follow-up)	WPAI	Scores and coded variables will be derived as described in Appendix D.
Secondary Outcomes (Initial Care and Follow-up)	SF-12	SF-12 sub-scores and total scores will be compiled using the Health Outcomes Scoring Software 5.0 by QualityMetric Inc. Further detail can be found in Appendix E.
Adverse Events (Baseline, Initial Care and Follow-up)	Highest severity AE	Severity of most severe AE for the patient with order of severity: Severe>Moderate>Mild Patients who only have AEs reported with missing severity,

Analysis Section (Visit)	Variable (Units)	Definition
		highest severity AE will be reported as missing

[Redacted]

[Redacted]

[Redacted]

[Redacted]

[Redacted]

[Redacted]

[Redacted]

[Redacted]

[Redacted]

[Redacted]

[Redacted]

[Redacted]

[Redacted]

[Redacted]

[Redacted]

[Redacted]

[Redacted]

[Redacted]

[Redacted]

[Redacted]

[Redacted]

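### SAP 6.2.5.2 limits infection-related hospital days to patients who had such a stay, so the outcome as written is not days per ABSSSI patient

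*SAP*

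**What the plan says.** The paragraph on this outcome in SAP 6.2.5.2 makes three statements about population.

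- It opens with the FAS: "Infection-related total admitted hospital days will be calculated by two methods by the pre-period and post-period for the FAS population". One method counts inpatient stays only; the other adds prolonged observation.
- It then says the days "will be assessed using a similar approach described for the primary analysis and will limit to patients who had infection-related hospital stays".
- It ends with a repeat: "Summaries will be repeated for only patients that are admitted", and rules out formal hypothesis testing.

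Appendix B (Hospitalization LOS) sums end date minus start date plus 1 over all stays that have both dates. Its infection-related version reads: "Subset all-cause hospitalization time for patients with infection-related hospitalization stays". It gives no value for a patient without such a stay.

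The objective (SAP 2.2), the definition (SAP 4.4) and protocol Table 3 (section 3.1.2) place no restriction on which patients contribute. SAP 4.4 totals the length of infection-related hospitalizations over the 44 days.

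The preceding paragraph of 6.2.5.2, on all-cause hospital days, uses the FAS, has a 0-day category, and repeats the summary for completers and for admitted patients. It still treats days as the main endpoint: "Patient counts and percentages will be given for the primary outcome".

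**The concern.** The pathway is meant to avoid admissions. Whether a patient has an infection-related stay is determined after enrolment and is what the pathway tries to alter. A summary limited to patients with a stay compares two groups selected on that event. If the pathway keeps some patients out of hospital, those patients leave the post-period summary instead of contributing 0 days. What remains is stay length given a stay, which is a different quantity from the one in the objective.

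Two further defects sit in the same text. First, Appendix B selects patients, not stays, so the unrelated hospital days of a patient who also had one infection-related stay could be counted, contrary to SAP 4.4. Second, the pointer to the primary analysis is outdated. The primary analysis is now a one-sided chi-square test on a proportion (SAP 6.2.6.1), which does not apply to days and does not fit a paragraph that excludes formal testing.

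**Working it through.** **The plan's own figure.** The SAP gives no figure for infection-related days. The only usable rates are the 38% and 23% initial admission rates in SAP 6.1.2. The power statement attached to them reproduces: a one-sided 5% test with 80% power needs [1.645·√(2·0.305·0.695) + 0.842·√(0.38·0.62 + 0.23·0.77)]² / 0.15² ≈ 116 per period. At 161 per period power is 90.2%, and at 145 (10% attrition) it is 87.4%. The primary outcome is not affected by this point.

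**Assumptions for the illustration.** The 38% and 23% stand in for the share with any infection-related stay over 44 days, and 161 per period stands in for the FAS. Mean stay among patients with a stay is not given, so let r be its post/pre ratio.

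**Patients left out by the limit.** Pre-period: 161 × (1 − 0.38) = 99.8, about 100. Post-period: 161 × (1 − 0.23) = 124.0. About 61 and 37 remain.

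**Identity.** Mean days per patient = share with a stay × mean days among those with a stay. Therefore:

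- restricted change = r − 1
- all-patient change = (0.23/0.38)·r − 1 = 0.6053·r − 1

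| r | Restricted mean | Days per patient |
|---|---|---|
| 0.8 | −20% | −51.6% |
| 1.0 | 0% | −39.5% |
| 1.2 | +20% | −27.4% |
| 1.8 | +80% | +8.9% |

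The signs differ only when r is above 1 and below 0.38/0.23 = 1.65.

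**Sensitivity to later stays.** If 5 points more per period have a later infection-related stay (43% and 28%), the upper bound is 0.43/0.28 = 1.54 and the equal-stay reduction is 34.9%. With 10 points more (48% and 33%), they are 0.48/0.33 = 1.45 and about 31%.

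**Shape of an all-patient summary, inpatient-only method.** At the planned rates 62% and 77% of patients have 0 days. Both medians are 0, and because 77% exceeds 75% the post-period upper quartile is 0 as well, so its box collapses. With 5 or 10 points more, the zero shares are 57% and 72%, or 52% and 67%: the medians stay at 0 but the post-period upper quartile does not. The observation-inclusive method would lower the zero shares by an unknown amount.

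**Appendix B.** For a patient with *a* infection-related days and *b* unrelated days, SAP 4.4 gives *a*; the literal Appendix B wording can give *a* + *b*.

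**The case against.** The strongest reply is that this is leftover wording. SAP 5.0 records that hospital days were formerly the primary outcome, so the pointer may mean the preceding paragraph, with its FAS base and 0-day category. On that reading the intention is sound, and an all-cause sum over no stays is naturally 0. This explains the pointer but not the limit, which then contradicts the pointer in its own sentence. Nor can the limit easily be read as selecting stays, because both 6.2.5.2 and Appendix B say patients. The layout may be settled elsewhere ("Table shells are included in the file"), but that file is not among the documents.

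A reader might cite "Table 13.1 Secondary Outcomes by All Patients: Full Analysis Set" and "Figure 2 Box plot of infection-related hospitalization time during initial care and follow-up by period: Full Analysis Set" as proof of an all-patient analysis. They are weak support. In that list, all patients means sites pooled, as the by-site tables that follow show, and a FAS label names the source population without excluding a subset summary. The closing repeat is also weak evidence, since admitted may mean admitted at the initial episode, a different subset from patients with any infection-related stay.

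It stands that the impact is limited. The outcome is descriptive and untested, and SAP 6.2 calls any secondary testing exploratory. Avoided admissions still appear in the primary outcome, in the all-cause days summary and in the infection-related hospitalization counts, which have a row for none. For the inpatient-only method, a reader could rebuild days per patient from the share with any such hospitalization times the restricted mean.

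It also stands that a blanket 0 would be wrong. Patients who discontinue early have unobserved time, SAP 5.0 reports attrition above the assumed 10%, and a stay with missing dates is not a stay of 0 days.

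**Conclusion.** The point holds for this one secondary outcome. Followed as written, 6.2.5.2 and Appendix B summarise stay length among patients with an infection-related stay, which does not answer the objective in SAP 2.2. At the planned rates and equal stay lengths, the restricted mean would show no change where days per patient fall about 39% (31% to 39% across the later-stay assumptions tried). This rests on initial admission rates standing in for 44-day stays and on a stay ratio that the documents do not give.

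A reader might infer that the trial will report a wrong direction, or that the pathway's effect will be hidden. The documents support neither. Opposite signs require a stay ratio between 1.00 and 1.65 (1.45 with 10 points of later stays), nothing shows which ratio applies, and the main effect on admissions is reported elsewhere. The primary analysis and sample size are unaffected. The wording should be corrected before analysis; the fault does not threaten the trial's main conclusion.

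**What to change.** In SAP 6.2.5.2:

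- Delete the limiting clause and the pointer to the primary analysis.
- State that the main summary covers all FAS patients, with 0 days for those with no recorded infection-related stay during their observed follow-up. Treat stays with missing dates as missing, not 0.
- Repeat the summary for completers with the existing Completers Flag in Appendix B, as is already planned for all-cause days.
- Keep the summary among patients with an infection-related stay as a labelled supplementary repeat.
- Report means and a 0-day category by period, because medians are likely to be 0. Show the Figure 2 box plot for patients with a stay, and label it so.

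In Appendix B, sum days only over stays flagged infection-related, in line with SAP 4.4.

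The cost is a few sentences of SAP text, one programming filter and the loss of an informative all-patient box plot. No new data are needed.

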1.4 Secondary objectives

Estimate the difference in the following outcomes during initial care (the date of enrollment to 14 days) and follow-up (30 days after initial care) comparing ABSSSI patients receiving care before implementation of the new critical pathway and after implementation:

- Total admitted hospital days during initial care and follow-up
- Infection-related total admitted hospital days during initial care and follow-up
- ED length of stay at initial episode of care (time from triage to release from ED)
- Infection-related major surgical interventions that required operating room time during initial care and follow-up (number of expected major surgeries, number of unexpected major surgeries, and total number of major surgeries)
- Infection-related hospitalizations during initial care and follow-up
- Infection-related hospitalizations during initial care and follow-up that resulted in admission to Intensive Care Unit (ICU)
- All cause hospitalizations in the 30 days post discharge from the hospital or release from the ED
- Infection-related ED visits during initial care and follow-up (number of expected, number of unexpected and number of total ED visits during initial care and follow-up)
- Infection-related outpatient healthcare visits (e.g., physicians' office visits, ED visits, infusion center visits, home health visits) during initial care and follow-up (number of expected visits, number of unexpected and total number of visits)
- Use of a PICC line or central line to administer antibiotic therapy during initial care and follow-up (number of patients who have a PICC or central line placed)
- Infection-related healthcare visits (e.g., hospitalizations, ED visits, other outpatient visits) due to PICC line or central line used to administer antibiotic therapy during initial care and follow-up (number of expected visits, unexpected visits and number of total visits)
- Serious adverse events (SAEs) during initial care and follow-up
- Patient satisfaction with care (subject reported)
- Patient work and productivity loss (subject reported)
- Patient Health-related Quality of Life (HRQoL) (subject reported)

2 Study design

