	All visits (unexpected and expected), by site (e.g., physicians' office visits, ED visits, infusion center visits, home health visits)
Use of PICC line or central line to administer antibiotic therapy during initial care and follow up	PICC line or central line placement for antibiotic therapy
Infection-related healthcare visits (e.g., hospitalizations, ED visits, other outpatient visits) due to PICC line or central line used	Unexpected visits due to PICC line (i.e. complications)
	Expected visits due to PICC line (i.e. initial placement, monitoring of PICC line)

Measure	Description
to administer antibiotic therapy during initial care and follow up	All visits due to PICC line (both unexpected and expected visits)
Serious adverse events (SAEs) during initial care and follow-up	All SAEs as defined in Section 5 Safety assessments
Patient satisfaction with care (subject reported)	Patient satisfaction with care (Subject-reported, Section 11.2- questionnaire similar to the final implemented version)
Patient work and productivity loss (subject reported)	Number of days with lost/reduced productivity during follow-up, as measured through Work Productivity and Activity Impairment Questionnaire (Section 11.4) ³⁰
Patient Health-Related Quality of Life (HRQoL) (subject reported)	Health-related quality of life (subject reported), as measured through the Medical Outcomes Study Short Form-12 (SF-12), with acute recall (1 week recall) (Section 11.5) ³¹

[figure not shown]

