2.2 Secondary Objectives

The secondary objectives of this study are to estimate the difference in the following outcomes during initial care (the date of enrollment to 14 days) and follow-up (30 days after initial care) comparing ABSSSI patients receiving care before implementation of the new critical pathway and after implementation:

- Total admitted hospital days during initial care and follow-up
- Infection-related total admitted hospital days during initial care and follow-up
- ED length of stay (LOS) at initial episode of care (time from triage to release from ED)
- Infection-related major surgical interventions that required operating room time during initial care and follow-up (number of expected major surgeries, number of unexpected major surgeries, and total number of major surgeries)
- Infection-related hospitalizations during initial care and follow-up
- Infection-related hospitalizations during initial care and follow-up that resulted in admission to Intensive Care Unit (ICU)

- All cause hospitalizations in the 30 days post discharge from the hospital or release from the ED
- Infection-related ED visits during initial care and follow-up (number of expected, number of unexpected and number of total ED visits during initial care and follow-up)
- Infection-related outpatient healthcare visits (e.g., physicians' office visits, ED visits, infusion center visits, home health visits) during initial care and follow-up (number of expected visits, number of unexpected and total number of visits)
- Use of a PICC line or central line to administer antibiotic therapy during initial care and follow-up (number of patients who have a PICC or central line placed)
- Infection-related healthcare visits (e.g., hospitalizations, ED visits, other outpatient visits) due to PICC line or central line used to administer antibiotic therapy during initial care and follow-up (number of expected visits, unexpected visits and number of total visits)
- Serious adverse events (SAEs) during initial care and follow-up
- Patient satisfaction with care (patient reported or completed by a caregiver if the patient cannot complete)
- Patient work and productivity loss (patient reported or completed by a caregiver if the patient cannot complete)
- Patient Health-related Quality of Life (HRQoL) (patient reported or completed by a caregiver if the patient cannot complete)

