Infection-related healthcare visits (e.g., hospitalizations, ED visits, other outpatient visits) due to PICC line or central line used to administer antibiotic therapy	Number of all, unexpected and expected infection-related healthcare visits due to PICC line or central line used to administer antibiotic therapy	Initial care and follow-up
Serious adverse events (SAEs)	Number of events, number of patients and percentage of patients experiencing SAEs as described in protocol	Initial care and follow-up
Patient satisfaction with care	Summarize patient satisfaction with care (reported by patient, questionnaire provided in protocol). This will be completed by a caregiver if the patient cannot complete.	Follow-up
Patient work and productivity loss	Number of days with lost/reduced productivity, as measured through the Work Productivity and Activity Impairment (WPAI) questionnaire. This will be completed by a caregiver if the patient cannot complete.	Follow-up

Measure	Definition	Period of Assessment
Patient HRQoL	Patient reported, as measured through the SF-12 ¹ (short-form), with acute recall (1-week recall). This will be completed by a caregiver if the patient cannot complete.	Initial care (in person) and follow-up (over phone). Change scores calculated for initial care

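### SAP 6.2.5.2 specifies the rows for PICC- and central-line-related visits with the wording of the outpatient-visit outcome, which conflicts with the outcome's definition and, taken literally, leaves out line-related hospitalizations

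*SAP*

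**What the plan says.** The outcome is defined consistently in four places.

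- Protocol 1.4 lists it among the secondary objectives and names the kinds of visit: "e.g., hospitalizations, ED visits, other outpatient visits) due to PICC line or central line".
- Protocol 3.1.2, Table 3, repeats that scope. It splits the count into unexpected, expected and all visits, and explains the first as "Unexpected visits due to PICC line (i.e. complications").
- SAP 2.2 carries the objective over: "Infection-related healthcare visits (e.g., hospitalizations, ED visits, other outpatient visits) due to PICC line or central line used to administer antibiotic therapy during initial care".
- SAP 4.4 names the measure as "Infection-related healthcare visits (e.g., hospitalizations, ED visits, other outpatient visits) due to PICC line or central line used to administer antibiotic therapy" and defines the count as "Number of all, unexpected and expected infection-related healthcare visits due to PICC line or central line used to administer antibiotic therapy".

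The analysis text is in SAP 6.2.5.2. The lead sentence of the relevant paragraph keeps the outcome: "Infection-related healthcare visits due to PICC line or central line used to administer antibiotic therapy will be displayed in tables by initial care, follow-up". The two sentences that set out the table rows then ask for patients with none, any, 1, 2 and three or more infection-related outpatient visits, and continue: "These categories will be repeated for all, expected, and unexpected outpatient healthcare visits".

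The paragraph specifies the full analysis set (FAS) and says that no formal hypothesis test will be done.

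**The concern.** The row sentences are the operative instruction for the table, and they describe a different outcome from the one in the heading and lead sentence. They differ from the definition in two ways: they restrict the count to outpatient visits, and they drop the requirement that the visit be due to a line.

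What is at stake is one descriptive secondary outcome. It bears on the rationale for the pathway, because Protocol 1.1.4 points out that dalbavancin can be given peripherally without a central or PICC line. Protocol Table 3 equates unexpected line-related visits with complications. An admission for a line complication is therefore squarely within what this outcome is meant to show.

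Post-period patients receive a single dose (Protocol 2.2.2). It is reasonable to infer, though the documents do not say so, that lines and line-related admissions would occur mainly in the pre-period. An omission would then fall unevenly on the two periods.

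**Working it through.** No stated figure has to be reproduced. The check is a comparison of texts.

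**Step 1: scope by place.**

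| Place | Kinds of visit | Tied to a PICC or central line? |
|---|---|---|
| Protocol 1.4 | hospitalizations, ED, other outpatient | yes |
| Protocol Table 3 | hospitalizations, ED, other outpatient | yes |
| SAP 2.2 | hospitalizations, ED, other outpatient | yes |
| SAP 4.4 | hospitalizations, ED, other outpatient | yes |
| SAP 6.2.5.2, lead sentence | healthcare visits, no restriction | yes |
| SAP 6.2.5.2, row sentences | outpatient visits only | not stated |

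**Step 2: source of the row wording.** The paragraph in SAP 6.2.5.2 for infection-related outpatient visits has the same row specification, word for word. By contrast, the paragraphs for infection-related hospitalizations, for those with ICU admission and for ED visits each use their own outcome's name in the row sentence. Only the line-related paragraph uses another outcome's name.

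**Step 3: is the narrowing declared?** SAP 5.0 lists the changes from the protocol-specified analyses: certain laboratory-based infection characteristics and the primary outcome. It mentions no change to line-related visits. Together with step 2, this points to a drafting slip and not to a design decision.

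**Step 4: what counts as outpatient.** SAP 4.4 gives office, ED, infusion center and home health visits as examples of outpatient visits. Hospitalizations are not among them. Of the three kinds named in the line-related outcome, two (ED and other outpatient) fall under outpatient and one (hospitalization) does not.

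**Step 5: possible readings of the paragraph.**

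- *Row sentences alone.* The table counts all infection-related outpatient visits. It duplicates the outpatient-visit table, includes visits that have nothing to do with a line, and contains no hospitalizations.
- *Row sentences limited by the lead sentence.* The table counts outpatient visits due to a line. It covers two of the three named kinds and omits hospitalizations.
- *Lead sentence and SAP 4.4 override the row sentences.* The table is right, but only because the row sentences are disregarded.

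Both readings that follow the row sentences lose line-related hospitalizations from this outcome.

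**Step 6: is the information restored elsewhere?** Infection-related hospitalizations and all-cause hospitalizations after discharge have their own tables in SAP 6.2.5.2. Adverse events that require hospitalization are SAEs (Protocol 4.4) and go into Table 14. Hospital stays are in Listing 8. Nothing in the visible text of these outputs attributes an admission to a line.

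**The case against.** The strongest reply is that no competent programmer would be misled. The heading and lead sentence of the same paragraph name the full outcome, and SAP 4.4 defines it. The rows are finally fixed in the table shells, which SAP 6.1.8 makes part of the plan and SAP 7.0 places in a separate file. Only the title of Table 13.1 can be seen, so the shell may already be right. The outcome is also descriptive, and SAP 6.2 treats secondary testing as exploratory.

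Much of this stands. The loss of events is conditional on a literal reading, and it cannot be said that the shell repeats the slip. The reply does not remove the contradiction, however. The SAP gives two incompatible instructions for one outcome, and SAP 6.1.8 says that analyses will follow this text. The double programming in SAP 6.1.9 is weak protection if both programmers work from the same sentences.

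A reader might infer more than the documents support:

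- *That line-related admissions would vanish from the trial's results.* They would not. They remain in the hospitalization and SAE outputs, and what is lost is the attribution to the line.
- *That ED visits for line complications are lost as well.* They are not, because the SAP counts ED visits as outpatient visits.
- *That reporting on the FAS only is a further defect, to be cured by a table for patients with a line.* The secondary outcomes in 6.2.5.2 are specified for the FAS. Having a line placed is a decision after enrollment that the pathway may itself change, so such a subset would not be comparable between periods.
- *That separate rows by setting are owed.* Protocol Table 3 asks only for unexpected, expected and all visits.

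**Conclusion.** The row specification in SAP 6.2.5.2 contradicts the definition of a named secondary outcome and should be corrected. If it is followed as written, the outcome either becomes a copy of the outpatient-visit table or omits one of its three named components, hospitalizations.

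The conclusion about wording rests only on the text and is firm. The conclusion about lost events assumes that the rows are programmed from the two sentences as they stand, which cannot be checked without the shells.

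The number of admissions affected cannot be derived: the documents give neither a rate of line placement nor a rate of line-related admission. The primary outcome, its test, the sample size and the error rate are untouched.

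**What to change.** In the line-related paragraph of SAP 6.2.5.2, change the object of both row sentences. Each should refer to infection-related healthcare visits (hospitalizations, ED visits and other outpatient visits) due to a PICC or central line. Keep the existing categories, the repetition for all, expected and unexpected visits, and the FAS.

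Then check the Table 13.1 shell against the corrected text and align it if needed.

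The cost is two reworded sentences and one check of a shell. No new analysis is required by this change.
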